5.2. Baseline Definitions

For all safety endpoints, the baseline value for the OLI phase, Injection Phase and Follow-up Phase, respectively, will be derived as follows:

Parameter	Phase	Study Assessments Considered as Baseline
Clinical Chemistry, Haematology, Coagulation, Vital Signs (pre-dose), ECG (pre-dose) ¹	OLI Phase	OLI Baseline = last non-missing pre-dose assessment collected <= Date of first OLI dose
	Injection Phase	Injection Phase Baseline = last non-missing assessment collected <= Date of first CAB injection, and > Date of last OLI dose
	Follow-up Phase	Follow-up Phase Baseline = last non-missing assessment collected <= Date of Nominal Follow-up Week 4 Visit [for Part 1 participants] / Date of Nominal Follow-up Week 12 Visit [for Part 2 participants]

- Average of the triplicate assessments for quantitative assessments and the worst-case of the triplicate assessments for qualitative assessments will be used as the baseline.

If time is not collected, Day 1 assessments are assumed to be taken prior to first dose of the respective phase.

Unless otherwise stated, if baseline data is missing no derivation will be performed and baseline will be set to missing.

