	If actual “Time of Day” for the assessment/event is not collected: For participants receiving second CAB injection: Date of First CAB Injection ≤ AE Start Date < Date of Second CAB Injection For participants not receiving second CAB injection: Date of First CAB Injection ≤ AE Start Date ≤ Date of Nominal Follow-up Week 4/Day 28 Visit [for Part 1 participants]/ Nominal Follow-up Week 12 Visit [for Part 2 participants]
Injection 2	If actual “Time of Day” for the assessment/event is collected: Date & Time of Second CAB Injection ≤ AE Start Date & Time and AE Start Date ≤ Date of Nominal Follow-up Week 4/Day 28 Visit [for Part 1 participants]/ Nominal Follow-up Week 12 Visit [for Part 2 participants] If actual “Time of Day” for the assessment/event is not collected: Date of Second CAB Injection ≤ AE Start Date ≤ Date of Nominal Follow-up Week 4/Day 28 Visit [for Part 1 participants]/ Nominal Follow-up Week 12 Visit [for Part 2 participants]
Follow-up	AE Start Date > Date of Nominal Follow-up Week 4/Day 28 Visit [for Part 1 participants]/ Nominal Follow-up Week 12 Visit [for Part 2 participants]
For Injection Site Reaction Adverse Events (Where collected on the ISR form for study treatment associated reactions, including drug related and non-drug related)	
Injection 1	If actual “Time of Day” for the assessment/event is collected: For participants receiving second CAB injection: Date & Time of First CAB Injection ≤ AE Start Date & Time < Date & Time of Second CAB Injection For participants not receiving second CAB injection: Date & Time of First CAB Injection ≤ AE Start Date & Time If actual “Time of Day” for the assessment/event is not collected: For participants receiving second CAB injection: Date of First CAB Injection ≤ AE Start Date < Date of Second CAB Injection For participants not receiving second CAB injection: Date of First CAB Injection ≤ AE Start Date

Injection 2	If actual "Time of Day" for the assessment/event is collected:
	Date & Time of Second CAB Injection ≤ AE Start Date & Time and AE Start Date
	If actual "Time of Day" for the assessment/event is not collected:
	Date of Second CAB Injection ≤ AE Start Date
For PK Data	
Study Period	Data Range
OLI	Excluding Injection 1 Day 1 Pre-dose Samples: Start Date & Time < Date & Time of First CAB Injection

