Injection 1	If actual "Time of Day" for the assessment/event is collected: For participants receiving second CAB injection: Date & Time of First CAB Injection ≤ Date & Time < Date & Time of Second CAB Injection For participants not receiving second CAB injection: Date & Time of First CAB Injection ≤ Date & Time and Date ≤ Date of Nominal Follow-up Week 4/Day 28 Visit [for Part 1 participants]/ Nominal Follow-up Week 12 Visit [for Part 2 participants] If actual "Time of Day" for the assessment/event is not collected:

	
For ECG (inj 2 Day 1 pre-dose), Vital Signs (inj 2 Day 1 pre-dose), PK (inj 2 Day 1 pre-dose), Labs (inj 2 Day 1) Assessments: ^a
 
Date of First CAB Injection ≤ Date ≤ minimum of (Date of Second CAB Injection, Date of Nominal Follow-up Week 4/Day 28 Visit [for Part 1 participants]/ Nominal Follow-up Week 12 Visit [for Part 2 participants])
 
For Other Assessments/Events:
 
For participants receiving second CAB injection: Date of First CAB Injection ≤ Date < Date of Second CAB Injection
 
For participants not receiving second CAB injection: Date of First CAB Injection ≤ Date ≤ Date of Nominal Follow-up Week 4/Day 28 Visit [for Part 1 participants]/ Nominal Follow-up Week 12 Visit [for Part 2 participants]

Injection 2	Date of Second CAB Injection ≤ Date ≤ Date of Nominal Follow-up Week 4 Visit [for Part 1 participants]/ Nominal Follow-up Week 12 Visit [for Part 2 participants]
Follow-up	Date > Date of Nominal Follow-up Week 4 Visit [for Part 1 participants]/ Nominal Follow-up Week 12 Visit [for Part 2 participants]
For Preference Questionnaire (Cohort 4b)	
Study Period	Date range
Injection 2	Date ≥ Date of Nominal Follow-up Week 4 Visit

NOTES:

- Date = Date of assessment
- a. Pre-dose based on nominal planned timepoint variable (PTM)

Table 6 Study Phases for Concomitant Medication

Concomitant during:	Date range
Prior	Medication Taken < OLI Treatment Start Date
OLI	
For participants continuing into Injection Phase: OLI Treatment Start Date & Time ≤ Medication Taken < Injection Phase Treatment Start Date & Time
 
For participants not continuing into Injection Phase: Medication Taken ≥ OLI Treatment Start Date & Time

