2.9.	Safety	AE5B	Summary of Adverse Events by System Organ Class and Preferred Term and Maximum Grade – Part 1 & Part 2	Include pooled treatment groups by dose & route	Cohort 1-5 IA Cohort 1-4, Cohort 1-5, EOS
2.10.	Safety	AE5B	Summary of Drug-Related Adverse Events by System Organ Class and Preferred Term and Maximum Grade – Part 1 & Part 2	Include pooled treatment groups by dose & route	Cohort 1-5 IA Cohort 1-4, Cohort 1-5, EOS
2.11.	Safety	ESI1	Summary of Characteristics of Seizures		Cohort 1-5, EOS
COVID-19 Assessment					
2.12.	Safety	PAN1	Summary of COVID-19 Assessments for Subjects with COVID-19 Adverse Events – Part 1 & Part 2		Cohort 1-5, EOS
2.13.	Safety	PAN2	Summary of COVID-19 Additional Assessments for Subjects with COVID-19 Adverse Events – Part 1 & Part 2		Cohort 1-5, EOS
2.14.	Safety	PAN3	Summary of COVID-19 Symptoms for Subjects with COVID-19 Adverse Events – Part 1 & Part 2		Cohort 1-5, EOS

CONFIDENTIAL

212482

Safety: Tables					
No.	Population	GSK Standard/ Example Shell	Title	Programming Notes	Deliverable [Priority]
2.15.	Safety	PAN4	Summary of COVID-19 Pandemic Visit Impacts – Part 1 & Part 2		Cohort 1-5, EOS
Laboratory: Chemistry					
2.16.	Safety	LB1	Summary of Clinical Chemistry Values – Part 1 & Part 2		Cohort 1-5, EOS
2.17.	Safety	LB1	Summary of Clinical Chemistry Changes from Baseline – Part 1 & Part 2		Cohort 1-5, EOS
2.18.	Safety	LB16A	Summary of Clinical Chemistry Results by Maximum Grade Increase Post-Baseline Relative to Baseline – Part 1 & Part 2	Unscheduled visits are included for determining maximum grade	Cohort 1-5 IA Cohort 1-4, Cohort 1-5, EOS
Laboratory: Hematology					
2.19.	Safety	LB1	Summary of Hematology Values – Part 1 & Part 2		Cohort 1-5, EOS
2.20.	Safety	LB1	Summary of Hematology Changes from Baseline – Part 1 & Part 2		Cohort 1-5, EOS
2.21.	Safety	LB16A	Summary of Hematology Results by Maximum Grade Increase Post-Baseline Relative to Baseline – Part 1 & Part 2	Unscheduled visits are included for determining maximum grade	Cohort 1-5 IA Cohort 1-4, Cohort 1-5, EOS
Laboratory: Coagulation					
2.22.	Safety	LB1	Summary of Coagulation Values – Part 1 & Part 2		Cohort 1-5, EOS
2.23.	Safety	LB1	Summary of Coagulation Changes from Baseline – Part 1 & Part 2		Cohort 1-5, EOS
2.24.	Safety	LB16A	Summary of Coagulation Results by Maximum Grade Increase Post-Baseline Relative to Baseline – Part 1 & Part 2	Unscheduled visits are included for determining maximum grade	Cohort 1-5, EOS
ECG					

Safety: Tables					

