No.	Population	GSK Standard/ Example Shell	Title	Programming Notes	Deliverable [Priority]
2.25.	Safety	SAFE_T1 (See EG1)	Summary of ECG Findings – Part 1 & Part 2–	Unscheduled visits are included for determining worst-case post-baseline	Cohort 1-5, EOS
2.26.	Safety	EG2	Summary of ECG Values – Part 1 & Part 2		Cohort 1-5, EOS
2.27.	Safety	EG2	Summary of ECG Changes from Baseline – Part 1 & Part 2		Cohort 1-5, EOS
2.28.	Safety	SAFE_T2 (See EG10A)	Summary of Maximum QTc Values Post-Baseline Relative to Baseline by Category – Part 1 & Part 2	Unscheduled visits are included for determining maximum QTc values	Cohort 1-5 IA Cohort 1-4, Cohort 1-5, EOS
2.29.	Safety	SAFE_T3 (See EG11)	Summary of Maximum Increase in QTc Values Post-Baseline Relative to Baseline by Category – Part 1 & Part 2	Unscheduled visits are included for determining maximum increase in QTc values	Cohort 1-5 IA Cohort 1-4, Cohort 1-5, EOS
Vital Signs					
2.30.	Safety	VS1	Summary of Vital Sign Values - Part 1 & Part 2		
2.31.	Safety	VS1	Summary of Vital Sign Changes from Baseline – Part 1 & Part 2		Cohort 1-5, EOS
2.32.	Safety	SAFE_T4 (See VS3)	Summary of Vital Sign Results Relative to Potential Clinical Importance (PCI) Criteria Post-Baseline Relative to Baseline – Part 1 & Part 2	Unscheduled visits are included for determination of 'to Low' and 'to High'	Cohort 1-5 IA Cohort 1-4, Cohort 1-5, EOS
Liver Events					
2.33.	Safety	LIVER1	Summary of Liver Stopping Event Reporting – Part 1 & Part 2		Cohort 1-5 IA Cohort 1-4, Cohort 1-5, EOS

Safety: Tables					
No.	Population	GSK Standard/ Example Shell	Title	Programming Notes	Deliverable [Priority]
2.34.	Safety	LIVER10	Summary of Hepatobiliary Laboratory Abnormalities – Part 1 & Part 2	Unscheduled visits are included	Cohort 1-5, EOS
Questionnaires					
2.35.	Safety	SAFE_T5	Summary of Numeric Rating Scale – Part 1 & Part 2	For each period: by visit, maximum and AUC. AUC not needed for Cohort 1-5 IA	Cohort 1-5 IA Cohort 1-4, Cohort 1-5, EOS
2.36.	Safety	SAFE_T6	Summary of Perception of Injection – Part 1 & Part 2		Cohort 1-5 IA Cohort 1-4, Cohort 1-5, EOS
Injection Site Area & Duration by Grade					
2.37.	Safety	SAFE_T7a	Event-Level Summary of Duration (Days) at Each Grade by Injection Site Reaction Preferred Term – Part 1 & Part 2	Injection 1 and Injection 2 periods only. Include pooled treatment groups by dose & route	Cohort 1-5 IA Cohort 1-4, Cohort 1-5, EOS

Safety: Tables					

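### Follow-up columns for chemistry and haematology use a baseline normally taken after injection, so a persisting abnormality reads as no change or no grade increase; the gap matters most in Tables 2.18 and 2.21 at the Cohort 1-5 interim

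*SAP*

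**What the plan says.** SAP 5.2 sets one baseline per phase for all safety endpoints.

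- Injection Phase: "Injection Phase Baseline = last non-missing assessment collected <= Date of first CAB injection, and > Date of last OLI dose". This is the pre-injection level.
- Follow-up Phase, Part 1: "Follow-up Phase Baseline = last non-missing assessment collected <= Date of Nominal Follow-up Week 4 Visit [for Part 1 participants". Part 2 uses the nominal Follow-up Week 12 visit. The rule does not require the value to precede any injection.

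SAP 10.4.1, Table 5, starts the follow-up period for laboratory data strictly after the same visit: "Date > Date of Nominal Follow-up Week 4 Visit [for Part 1 participants]/ Nominal Follow-up Week 12 Visit [for Part 2 participants". The Week 4 or Week 12 value itself belongs to the injection period. Adverse events follow the same cut, by onset: "AE Start Date > Date of Nominal Follow-up Week 4/Day 28 Visit [for Part 1 participants".

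SAP 5.1 lists Follow-up as a separate display entry for each arm. SAP 10.10.5 plans change-from-baseline tables for chemistry and haematology (2.17 and 2.20) and grade-increase tables (2.18 and 2.21). Table 2.18 is titled "Summary of Clinical Chemistry Results by Maximum Grade Increase Post-Baseline Relative to Baseline". No listed display sets follow-up laboratory values against the pre-injection baseline.

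**The concern.** Participants are followed for 52 weeks after the last injection because the drug is long-acting (Protocol 4.1.6), and liver biochemistry abnormalities are a secondary endpoint (SAP 2.2). Follow-up is where a reader would judge whether a laboratory change caused by the injections has persisted or resolved. Protocol 8.2.4 and Appendix 6 likewise describe resolution partly as a return to baseline. A reference value taken after injection cannot show return to the level before it.

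The Cohort 1-5 interim is run to disseminate results and includes complete follow-up for Cohorts 1-3, which is 3 x 20 = 60 planned participants (SAP 3.2). Its summary columns could leave a reader unable to tell persistence from normality during follow-up.

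**Working it through.** The plan states no figure here, so the check traces the rule and applies it to assumed profiles.

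**1. When the follow-up baseline is taken.** Protocol 4.1.6 places the follow-up visits at Weeks 4, 8, 12, 20, 28, 36, 44 and 52 after the last injection in Part 1, and at Weeks 12, 24, 40 and 52 in Part 2. The schedules in SAP 10.2 include chemistry and haematology at Week 4 (Part 1) and Week 12 (Part 2). The baseline is normally that visit's value. If it is missing, the rule falls back to an earlier value, usually still after an injection.

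**2. Formulas.** Let P be the pre-injection value, R the Week 4 or 12 value, F a later follow-up value and g(.) the grade.

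- Injection column: R - P.
- Follow-up column as planned: F - R, with grade increase g(F) - g(R) if positive.
- Follow-up against pre-injection: F - P = (F - R) + (R - P), with grade increase g(F) - g(P) if positive.

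ALT grades come from SAP 10.8.1: Grade 1 from 1.25 x ULN and Grade 2 from 2.5 to below 5.0 x ULN. The ALT values below (x ULN) are assumptions, all below the 3 x ULN stopping criterion in Protocol Appendix 6.

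| Course | P | R | F | Injection column | Follow-up as planned (grade increase) | Against pre-injection (grade increase) |
|---|---|---|---|---|---|---|
| Persists | 0.8 | 2.6 | 2.6 | +1.8 | 0.0 (0) | +1.8 (2) |
| Full recovery | 0.8 | 2.6 | 0.8 | +1.8 | -1.8 (0) | 0.0 (0) |
| Partial recovery | 0.8 | 2.6 | 1.5 | +1.8 | -1.1 (0) | +0.7 (1) |
| Rises within a grade | 0.8 | 2.6 | 2.9 | +1.8 | +0.3 (0) | +2.1 (2) |
| Rises across a grade | 1.0 | 2.0 | 2.7 | +1.0 | +0.7 (1) | +1.7 (2) |
| Never changes | 0.8 | 0.8 | 0.8 | 0.0 | 0.0 (0) | 0.0 (0) |

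The first and last rows have the same follow-up entry. In the fifth row the further grade rise is counted, but as one grade and not two.

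**3. What else is delivered.**

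- Formal reports: value Tables 2.16 and 2.19, change Tables 2.17 and 2.20, Table 2.34 ("Summary of Hepatobiliary Laboratory Abnormalities"), and Listings 26 and 27 for participants with any toxicity.
- Cohort 1-5 interim: for chemistry and haematology, only Tables 2.18 and 2.21, with liver-stopping Table 2.33. The items in the previous bullet are not interim deliverables.
- Interim adverse event displays: Tables 2.9 ("Summary of Adverse Events by System Organ Class and Preferred Term and Maximum Grade") and 2.10, and Listing 17. A laboratory event that began before the cut is counted by onset in an injection column, so these tables do not show its persistence in follow-up either.

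**4. How much of the schedule falls after the reset.** Scheduled post-injection chemistry and haematology assessments judged against the later baseline are:

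- two-injection Part 1 cohorts: 5 / (6 + 5) = 45%;
- Cohort 4h: 5 / (5 + 5) = 50%;
- Cohort 5, with one injection: 3 / (10 + 3) = 23%.

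These are shares of the schedule, not error rates.

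**5. Creatinine (conditional).** SAP 10.8.1 grades creatinine partly by its ratio to the participant's baseline and names no phase. Assume 0.70 mg/dL before injection, 0.95 at Follow-up Week 4 and 1.20 at Week 36. Against pre-injection, 1.20 / 0.70 = 1.71, which is Grade 3 (1.5 to below 2.0). If SAP 5.2 governs, 1.20 / 0.95 = 1.26, below the 1.3 threshold. The grade then rests on the ULN criterion alone: with an assumed ULN of 1.0 to 1.3 mg/dL, 1.20 is 1.20 to 0.92 x ULN, so Grade 1 or 0.

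**The case against.** A baseline for each phase is a legitimate choice, and it answers a useful question: what changed after the injection phase? In the formal reports persistence can be read from the value tables, Table 2.34 and the listings. A mean total change can also be recovered by adding the injection and follow-up columns if the same participants contribute. The interim is preliminary, and SAP 2.3 records that Cohort 5 injections had been stopped and Cohort 6 judged unnecessary, so no dosing decision is shown to rest on these columns. The profiles above are invented. The table shells are in a separate document and could not be checked.

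Most of this stands and limits the point. It does not close the gap. Adding columns does not work for maximum grade increases, and at the interim there are no change or value tables to add or read. Interim Listing 17 may reveal an individual case if the change was recorded as an adverse event, but it is not a summary. SAP 5.1 also lists an Overall entry, but the plan does not say which baseline it uses, so it cannot be relied on.

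For vital signs the objection has real force. SAP 5.2 tags them as pre-dose. If that tag governs follow-up, the baseline is the pre-injection value in Cohorts 4h and 5, and the Injection 2 pre-dose value in the two-injection cohorts. Table 2.31, and Table 2.32 ("Summary of Vital Sign Results Relative to Potential Clinical Importance (PCI) Criteria Post-Baseline Relative to Baseline"), are affected as described only if the Week 4 or 12 reading is used.

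**Conclusion.** The point holds for the follow-up columns of Tables 2.17, 2.18, 2.20 and 2.21. Its practical weight lies in the grade-increase tables, above all 2.18 and 2.21 at the Cohort 1-5 interim. There, a Grade 2 ALT below the stopping criterion that arose after injection and persists appears in the injection columns but leaves no grade increase in the follow-up column. This is a worthwhile, inexpensive improvement, not an error that invalidates the safety analysis.

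Three stronger readings are not supported:

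- A reader might infer that post-injection abnormalities are hidden. They are not: the Week 4 or 12 value is compared with the pre-injection baseline in the injection columns.
- A reader might infer that worsening in follow-up is missed. A further grade rise is still counted; only its size from the pre-injection level is reduced.
- A reader might take the schedule shares as the proportion of results misreported. The distortion depends on how far each participant's reset value differs from the pre-injection value, and the documents give no information on that.

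The conclusion assumes that the Week 4 or 12 sample is usually available and that the displays follow the SAP text. Creatinine and vital signs are conditional, as set out above. Coagulation and ECG are outside the point: in Cohort 4h coagulation is scheduled before the dose and then only at Week 52, and no follow-up ECG is scheduled.

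**What to change.** In SAP 5.2, keep the phase-specific follow-up columns. Add follow-up change-from-baseline and maximum-grade-increase summaries for chemistry and haematology against the Injection Phase baseline, including Tables 2.18 and 2.21 at the Cohort 1-5 interim. State whether the follow-up baseline for vital signs is the Week 4 or 12 reading; if it is, make the same addition to Tables 2.31 and 2.32. State that creatinine ratio grading in follow-up uses the pre-injection baseline.

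The cost is SAP wording, one more baseline flag in the analysis dataset and a few more table columns. No new data are needed.

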5.3. Other Considerations for Data Analyses and Data Handling Conventions

Other considerations for data analyses and data handling conventions are outlined in the appendices:

Section	Component
10.1	Appendix 1: Exclusions from Per Protocol Population
10.2	Appendix 2: Schedule of Activities
10.3	Appendix 3: Assessment Windows
10.4	Appendix 4: Study Phases, Study Periods, and Treatment Emergent Adverse Events
10.5	Appendix 5: Data Display Standards & Handling Conventions
10.6	Appendix 6: Derived and Transformed Data
10.7	Appendix 7: Reporting Standards for Missing Data
10.8	Appendix 8: Values of Potential Clinical Importance
10.9	Appendix 9: Abbreviations & Trademarks
10.10	Appendix 10: List of Data Displays
10.11	Appendix 11: AEsI Identification

6. STUDY POPULATION ANALYSES

6.1. Overview of Planned Study Population Analyses

The study population analyses will be based on the “Safety” population, unless otherwise specified.

Study population analyses including analyses of participant’s disposition, protocol deviations, inclusion/exclusion criteria deviations, study populations, demographic and baseline characteristics, prior and concomitant medications, medical history, and exposure will be based on GSK Core Data Standards.

The details of the planned displays are provided in [Appendix 10: List of Data Displays](#).

7. SAFETY ANALYSES

The safety analyses will be based on the “Safety” population, unless otherwise specified.

7.1. Adverse Events Analyses

Adverse events analyses including the analysis of AEs, serious AEs (SAEs), injection site reaction related AEs, and other significant AEs will be based on GSK Core Data Standards. The details of the planned displays are provided in [Appendix 10: List of Data Displays](#).

Injection site reactions will be summarized by preferred term and by the following grouped terms: ‘Injection Site Induration/Swelling’, ‘Injection Site Pain/Tenderness’, ‘Injection Site Redness/Erythema’, ‘Injection Site Redness/Erythema/Pain/Tenderness/Induration/Swelling’.

For Cohort 4b, safety data will be summarized by period (OLI, injection 1, injection 2, follow-up, overall) where injection 1 and injection 2 data is aggregated across mitigation treatments CCI [REDACTED]

7.2. Adverse Events of Special Interest

A comprehensive list of MedDRA terms based on clinical review will be used to identify each type of event for Adverse Events of Special Interest (AESI). [Changes to the MedDRA dictionary may occur between the start of the study and the time of reporting and/or emerging data from ongoing studies may highlight additional AESIs, therefore the list of terms to be used for each event of interest and the specific events of interest will be based on the safety review team (SRT) agreements in place at the time of reporting.] The details of the current planned grouping, including Standardized MedDRA Query (SMQ) values (as applicable), and planned displays are provided in [Appendix 11: AESI Identification](#) and [Appendix 10: List of Data Displays](#).

7.3. Clinical Laboratory Analyses

Laboratory evaluations will be based on GSK Core Data Standards. The details of the planned displays are in [Appendix 10: List of Data Displays](#).

[figure not shown]
cc1

7.5.

CCI

CCI

CCI

CCI

7.5.3. Ordinal Endpoint / Variables

The following ordinal endpoint/variable will be analysed in the crossover analysis comparing preference for topical steroids vs topical NSAIDs for Cohort 4b:

Ordinal Endpoint/Variable

 • For the hypothesis test for evidence of a treatment difference (i.e., p-value), the 5-level ordinal endpoint for Injection Preference from the Preference Questionnaire will be coded as: 
 • -2 (strongly prefer injection 2 compared to injection 1) • -1 (slightly prefer injection 2 compared to injection 1) • 0 (no preference between injection 1 and injection 2) • 1 (slightly prefer injection 1 compared to injection 2) • 2 (strongly prefer injection 1 compared to injection 2)

